### **9.3.2 Baseline/Day 1 (Visit 1)**

Epoetin alfa dosing will have been stopped for a minimum of 5 days in the Main study or 2 days in the ESA hyporesponder parallel study until Baseline/Day 1.

On Baseline/Day 1, blood sample collection and other Baseline/Day 1 procedures will be completed prior to dosing with study drug (vadadustat or epoetin alfa). On Baseline/Day 1, study drug will be administered at the study site, and will be administered after the PK sample is collected and prior to the dialysis session.

At Baseline/Day 1, the following activities/procedures will be performed:

- Review of study eligibility criteria
- Review of acceptable methods of contraception
- Review of medical history for new conditions since SV2
- Review of medication use since SV2
- Randomization
- Introduction to and instruction on the use of the eDiary and paper dosing reminders
- SF-36v2, PGI-S, and EQ-5D-5L assessments
- Abbreviated, symptom-directed physical examination, at the discretion of the investigator, as clinically indicated
- 12-lead ECG: ECGs will be completed prior to blood draws when possible and will be obtained after the subject has been resting supine comfortably for approximately 5 minutes; ECG may be completed and reviewed by the investigator on Baseline/Day 1 or if needed for scheduling reasons (e.g., dialysis treatment is scheduled for early morning of Baseline/Day 1), the ECG can be completed and reviewed up to 1-3 days prior to Baseline/Day 1.
- Vital signs including temperature, HR, BP, and RR (assessed in seated position after 5 minutes of rest and prior to blood draws), and dry weight

- Laboratory Procedures:
  - CBC (including differential)
  - Reticulocyte count
  - CRP
  - Serum chemistry
  - LFTs
  - Iron indices
  - Lipid profile
  - Biomarkers (VEGF, and Hepcidin)
  - PK prior to vadadustat or epoetin alfa dosing (see [Section 9.2.2.1](#), PK/PD Sampling for Subjects Randomized to Vadadustat and [Section 9.2.2.2](#), PK Sampling for Subjects Randomized to Epoetin Alfa) and prior to the dialysis session
- Study drug assessments and procedures:
  - Subject will take/receive their first dose of study drug at the study site during Baseline/Day 1
  - For subjects in the vadadustat treatment arm only:
    - Initiate vadadustat dosing
    - Vadadustat drug dispensation
    - Review vadadustat dosing instructions
  - Epoetin alfa dosing will continue for the subjects in the epoetin alfa arm
  - Iron supplementation as needed to maintain ferritin  $\geq 100$  ng/mL or TSAT  $\geq 20\%$  (per local product label; see [Section 8.4.8](#), Iron Supplementation)
  - Visit registration in IWRS
- Safety assessments:
  - AE review as needed
  - Review use of rescue therapy (RBC transfusions and ESA therapy)

### **9.3.3 Visit 2 to Visit 13 (Weeks 1 to 20)**

At the Baseline/Day 1, Visit 7, and Visit 9, subjects in the vadadustat treatment arm will be reminded and instructed to hold their vadadustat dose on the day of Visit 2, Visit 8, and if applicable Visit 10, respectively, as blood sample for PK analysis will be collected on the day of Visit 2, Visit 8, and Visit 10 prior to vadadustat administration at the study site.

The following activities/procedures will be performed at Visit 2 to Visit 13, unless noted otherwise:

- SF-36v2, PGI-S, and EQ-5D-5L assessments (Visit 9 only)
- Abbreviated, symptom-directed physical examination, at the discretion of the investigator, as clinically indicated
- Vital signs including temperature, HR, BP, and RR (assessed in seated position after 5 minutes of rest and prior to blood draws). Dry weight will be collected at Visit 9 only.

- A status check (BP, vital signs, and review of current health status) will be performed during weeks with no scheduled study visit.
- Dialysis adequacy, as available from local information (Visit 9 only)
- Safety assessments:
  - AE review
  - Review use of rescue therapy (RBC transfusions and ESA therapy)
  - Review of therapeutic phlebotomy
- Laboratory procedures (if blood samples are collected on a day of dialysis, blood draws will be done prior to dialysis, if applicable):
  - CBC
  - Reticulocyte count (Visits 2, 4, 6, 8, 9, 10 and 12 only)
  - CRP (Visit 9 only)
  - Serum chemistry (Visit 9 only)
  - LFTs (Visits 3, 4, 5, 6, 7, 9, 11, 12, and 13)
  - Iron indices (Visits 4, 6, 9 and 12 only)
  - Biomarkers (VEGF and Hepcidin, Visit 9 only)
  - Vadarustat PK/PD sampling (Visits 2, 8 and 10 only) for details, see [Section 9.2.2.1](#), PK/PD Sampling for Subjects Randomized to Vadarustat and [Section 9.2.2.3](#), PK/PD Sampling)
  - Epoetin alfa PK sampling (Visit 2 only) for details, see [Section 9.2.2.2](#), PK Sampling for Subjects Randomized to Epoetin Alfa and Section 9.2.2.3, PK/PD Sampling)
- Medication assessments and procedures:
  - Assessment for meeting criteria to switch from daily to TIW dosing (vadarustat arm)
  - Review of concomitant medications
  - Subjects in epoetin alfa treatment arm will continue to receive epoetin alfa
  - For subjects in the vadarustat treatment arm only:
    - Visit registration in IWRS (for bottle dispensing only)
    - Vadarustat drug dispensation (scheduled Visits 4, 6, 9, and 12)
    - Review vadarustat dosing instructions
    - Review of vadarustat dosing compliance
    - Vadarustat reconciliation
  - Review of iron supplementation as needed to maintain ferritin  $\geq 100$  ng/mL or TSAT  $\geq 20\%$  (per local product label; see [Section 8.4.8](#), Iron Supplementation)

### 9.3.4 EOT Visit 14 (Week 20)

EOT evaluations will be performed when the Treatment Period (Baseline/Day 1 to Visit 13) is completed. Subjects who prematurely discontinue study drug for any reason will also attend this visit.

At Visit 14 (EOT), the following activities/procedures will be performed:

- SF-36v2, PGI-S, and EQ-5D-5L assessments
- Vital signs including, HR, BP, and RR (assessed in seated position after 5 minutes of rest and prior to blood draws), as well as temperature and dry weight
- Dialysis adequacy, as available from local information
- Safety assessments:
  - AE review
  - Review use of rescue therapy (RBC transfusions and ESA therapy)
  - Review of therapeutic phlebotomy
- Laboratory Procedures:
  - CBC (with differential)
  - Reticulocyte count
  - CRP
  - Serum chemistry
  - LFTs
  - Iron indices
  - Lipid panel
  - Biomarkers (VEGF and Hepcidin)
- Medication assessments and procedures:
  - Review of concomitant medications
  - Subjects in epoetin alfa treatment arm will continue to receive epoetin alfa.
  - For subjects in the vadadustat treatment arm only:
    - Review of vadadustat dosing compliance
    - Vadadustat reconciliation
    - Resume dosing with epoetin alfa (or another ESA): After the end of vadadustat treatment at Visit 14 (or following early discontinuation of vadadustat), subjects may resume dosing with epoetin alfa (or another ESA), based on standard of care.
  - Visit registration in IWRS
  - Review of iron supplementation as needed to maintain ferritin  $\geq 100$  ng/mL or TSAT  $\geq 20\%$  (per local product label; see [Section 8.4.8](#), Iron Supplementation)

### 9.3.5 Safety Follow-Up Visit 15 (Week 24)

At the Visit 15, the following activities/procedures will be performed:

- SF-36v2, EQ-5D-5L, PGI-S, and PGI-C assessments
- AE review
- Review use of rescue therapy (RBC transfusions and ESA therapy)
- Review use of therapeutic phlebotomy
- Concomitant medication review

### 9.3.6 Unscheduled Visits

Unscheduled assessments may be conducted at any time as medically warranted. All laboratory assessments required in the study are included in the central laboratory Unscheduled Visit kits to allow for re-testing of any study laboratory parameters. Additionally, the Unscheduled Visit kits include a coagulation panel (international normalized ratio [INR], prothrombin time (PT), and activated partial thromboplastin time [aPTT]) for testing INR (see Section 9.4, Study Medication Stopping Rules).

Starting from Baseline/Day 1, the following activities/procedures will be performed at an Unscheduled Visit at minimum:

- Safety assessments:
  - AE review
  - Review use of rescue therapy (RBC transfusions and ESA therapy)
  - Review of Therapeutic phlebotomy
- Medication assessments and procedures:
  - Review of concomitant medications
- Any other procedures that are medically warranted at the discretion of the investigator.

### 9.4 Study Medication Stopping Rules

Study medication must be permanently discontinued if a subject meets one of the following criteria in Table 2 below:

**TABLE 2 STUDY MEDICATION STOPPING RULES**

ALT or AST >3x ULN and total bilirubin >2x ULN	Permanently Discontinue Treatment
ALT or AST >3x ULN and INR >1.5	Permanently Discontinue Treatment
ALT or AST >8x ULN	Permanently Discontinue Treatment
ALT or AST remains >5x ULN over 2 weeks	Permanently Discontinue Treatment
ALT or AST >3x ULN with symptoms (e.g., fatigue, nausea, vomiting, right upper quadrant pain, fever, rash) or eosinophilia	Permanently Discontinue Treatment

ALT: alanine aminotransferase; AST: aspartate aminotransferase; INR: international normalized ratio; ULN: upper limit of normal

See [Section 10.1.1](#), AEs for reporting requirements related to a subject being permanently discontinued based on meeting the laboratory abnormalities list above in Table 2.

## 10 ADVERSE EVENTS

### 10.1 Definitions

#### 10.1.1 AEs

For the purposes of this study, an AE is any untoward medical occurrence (including an abnormal laboratory finding) that occurs in the protocol-specified AE reporting period; the event does not necessarily have a causal relationship with that treatment or usage.

An AE includes medical conditions, signs, and symptoms not previously observed in the subject that emerge during the protocol-specified AE reporting period, including signs or symptoms associated with pre-existing underlying conditions that were not present prior to the AE reporting period.

AEs therefore include the following:

- All AEs, whether suspected to be causally related to study drug or otherwise.
- All AEs secondary to any medication overdose, medication error, abuse, withdrawal, sensitivity, or toxicity.
- Illnesses apparently unrelated to study drug, including the worsening of a pre-existing illness (see paragraph below on Pre-existing Conditions).
- Injury or accidents. Note that if a medical condition is known to have caused the injury or accident (e.g., a fall secondary to dizziness), the medical condition (dizziness) and the accident (fall) will be reported as 2 separate AEs.
- Abnormalities in physiological testing or physical examination findings that require clinical intervention or further investigation (beyond ordering a repeat [confirmatory] test).
- Laboratory abnormalities that require clinical intervention or further investigation (beyond ordering a repeat [confirmatory] test) unless they are associated with an already reported clinical event. Laboratory abnormalities associated with a clinical event reported as an AE (e.g., elevated liver enzymes in a subject with jaundice) will be described under 'Comments' on the report of the clinical event rather than reported as separate AEs.

The following guidelines are to be used when reporting AEs for this study:

**Medical Diagnoses** – Whenever possible, a medical diagnosis term will be used to report AEs instead of signs and symptoms due to a common etiology, as determined by qualified medical study staff. For example, pneumonia will be the reported AE term, instead of fever and dyspnea, when the diagnosis has been established. Signs and symptoms will be reported as event terms only when the medical diagnosis remains unknown, and revised to a medical diagnosis term once it has been established.

**Procedures** – Diagnostic and therapeutic non-invasive and invasive procedures, such as surgery, will not be reported as AEs. However, the medical condition for which the procedure was performed will be reported if it meets the definition of an AE. For example, an acute appendicitis that begins during the AE reporting period will be reported as the AE and the resulting appendectomy noted under 'Comments'.

Pre-planned therapeutic procedures not associated with a new medical condition or worsening pre-existing condition will not be reported as AEs.

**Pre-existing Conditions** – In this study, a pre-existing condition (i.e., a disorder present before the AE reporting period started and noted on the pretreatment medical history/physical examination form) will not be reported as an AE unless the condition worsens or episodes increase in frequency during the AE reporting period.

**Abnormal Test Findings** – All laboratory test results will be reviewed by the investigator. The investigator will utilize his/her judgment in determining if out-of-range laboratory values are clinically significant and will denote this using the abbreviation “CS” on the laboratory report for source documentation. Laboratory tests that are labeled as clinically significant will be reported as AEs, either separately or as part of a description of a symptomatic AE. If there are significant changes in a laboratory report from a previous visit that are determined to be clinically significant, these will also be reported as AEs. Any abnormal laboratory value which requires treatment or further diagnostic testing and/or results in discontinuation from study will be reported as an AE. An expected laboratory abnormality from a condition that is part of the medical history is not considered clinically significant for the purposes of the study unless it represents a worsening of the condition.

**Abnormalities in ALT, AST and Total Bilirubin** – Abnormalities in ALT, AST, and total bilirubin should be reported to the sponsor’s Medical Monitor or Contract Research Organization (CRO) designee within 24 hours of awareness as an SAE with “medical significance” criteria selected, if the following conditions are met:

- New elevation in ALT or AST  $>3$  times ULN, with or without an elevation of total serum bilirubin  $>2$  times ULN; AND

If new elevations in ALT or AST  $>3$  times ULN, **without** an elevation of total serum bilirubin  $>2$  times ULN and without meeting any criteria listed in [Table 2](#) are identified, the following steps are to be taken:

- Temporary discontinuation of study medication;
- Repeat testing of ALT, AST, ALP, and total bilirubin, should be completed within 48 to 72 hours to confirm the abnormalities and to determine trend;
- Study medication should not be resumed until monitoring indicates abnormalities have resolved or have stabilized.

Details on the management of subjects with other ALT and AST abnormalities are further described in [Section 9.4](#), Study Medication Stopping Rules.

**Worsening of Anemia** – In this study, it is possible that some subjects may experience a worsening of anemia. As the primary endpoint of this study assesses Hb response, worsening of anemia is captured as part of this efficacy parameter. Worsening of anemia will not be considered an AE unless the worsening of anemia is associated with a cause *other than* the subject’s CKD.

**Transplantation** – During this study, it is anticipated that subjects may receive a kidney transplant. These events will not be recorded as AEs. Subjects will discontinue study drug for receipt of a kidney, other solid organ, hematopoietic stem cell or bone marrow transplant, will complete the EOT visit (Visit 14) assessments and will complete the Safety Follow-Up (Visit 15) 4 weeks after Visit 14 as described in [Section 7.6.3](#), Early Discontinuation from Study.

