A 16-week, open-label, multicenter, Phase 2 trial evaluated vadadustat in 94 subjects receiving chronic hemodialysis previously maintained on epoetin alfa and IV iron form the 3 months prior to Screening (Study AKB-6548-CI-0011 [CI-0011]). Subjects were assigned to one of three vadadustat dose cohorts: 300 mg daily, 450 mg daily, or 450 mg three times a week (TIW). Dosing was fixed for the first 8 weeks; for the subsequent 8 weeks dose was adjusted from 150 to 600 mg according to Hb response based upon a dose adjustment algorithm. Sixty-nine of the 94 subjects completed the study. The primary endpoint was the mean Hb concentration change from pre-treatment average (Screening Visit 1, Screening Visit 2, and Baseline Visit) to mid-study (Weeks 7 to 8) and end-of-study (Weeks 15 to 16) and was analyzed using observed Hb values (no imputation for missing data). No statistically significant mean change in Hb from pre-treatment average was observed for either of the two time points for any of the three treatment groups.

Among subjects randomized to an initial dose of 300 mg daily, 450 mg daily, or 450 mg TIW, 0% (0 of 30), 3% (1 of 33), and 19% (6 of 31) of subjects withdrew from the study due to worsening anemia, respectively. In a sensitivity analysis using last observation carried forward (LOCF) for the primary efficacy endpoint, no significant mean change in Hb from pre-treatment levels was observed in the 300 mg daily dosing group. At Weeks 15 to 16, modest, statistically significant mean decreases were observed in the 450 mg daily and 450 mg TIW dosing groups.

In a post-hoc univariate analysis of baseline characteristics, higher pre-baseline epoetin alfa dose was associated with a decrease in mean Hb at Weeks 7 to 8 and Weeks 15 to 16 in the dosing cohorts. Subjects who discontinued the study due to worsening anemia had a higher mean pre-

baseline epoetin alfa dose compared with subjects who discontinued due to other reasons or subjects who completed the study.

Based on Phase 1 and Phase 2 study results, vadadustat appears to be a suitable candidate for continued development as a treatment for anemia in patients with CKD.

In the ongoing global Phase 3 and Japanese Phase 3 clinical studies, over 7000 subjects are planned to be treated with vadadustat or comparator.

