### 10.1.2 SAEs

Each AE is to be classified by the investigator as SERIOUS or NONSERIOUS. An AE that meets 1 or more of the following criteria/outcomes is classified as serious:

- Death
- Life-threatening
  - Life-threatening is defined as any event in which the subject was at risk of death at the time of the event; ‘life-threatening’ does not refer to an event which hypothetically might have caused death if it were more severe. For example, drug-induced hepatitis that resolved without evidence of hepatic failure would not be considered life threatening, even though drug-induced hepatitis of a more severe nature can be fatal.
- In-patient hospitalization or prolongation of existing hospitalization
  - Hospitalization is defined as an overnight admission with observation of a minimum of 24 hours. A hospitalization planned before the start of the study for a pre-existing condition that has not worsened during the AE reporting period does not constitute an SAE unless an untoward event occurs related to the procedure (e.g., elective hospitalization for a total knee replacement due to a preexisting condition of osteoarthritis of the knee that has not worsened during the course of the study).
- Persistent or significant disability/incapacity
  - Disability is defined as a substantial disruption in a person’s ability to conduct normal life functions.
- Congenital anomaly/birth defect
- Is considered a medically important event not meeting the above criteria, but which may jeopardize a subject, or may require medical or surgical intervention to prevent one of the criteria listed in this definition.

Serious also includes any other event that the investigator or sponsor judges to be serious. If there is any doubt whether the information constitutes an AE or SAE, the information is to be treated as an SAE.

In addition to the above criteria for classifying AEs as serious, the following situations will also be classified as serious for purposes of this study:

- Malignancies – Newly diagnosed malignancies or a recurrence of a malignancy will be reported as an SAE with the seriousness criterion “medically important” if no other seriousness criteria are met. If a subject develops basal cell carcinoma of skin, squamous cell carcinoma of skin, or cervical carcinoma in situ during the study, or has worsening of these events from baseline, the investigator will determine if the event is reported as an AE or SAE.

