#### **10.3.4 Relationship to Study Drug**

The causal relationship of the AE to study drug (vadadustat or epoetin alfa) will be assessed by both the investigator and the sponsor.

The assessment of causal relationship to study drug will be evidence-based, and not based on the premise that all AEs are possibly causally related to study drug until proven otherwise.

Examples of evidence that would suggest a causal relationship between the study drug and the AE include the occurrence of an AE that is uncommon and known to be strongly associated with drug exposure (e.g., angioedema, hepatic injury, and Stevens-Johnson syndrome) or an AE that is uncommon in the population exposed to the drug.

The causal relationship of the AE is assessed using a binary system, and AEs are classified as either 'related' or 'unrelated';

Related: There is 'reasonable possibility' that the drug caused the AE. The AE follows a reasonable temporal sequence from the time of drug administration. There is supportive evidence (facts) to suggest a possible causal relationship, irrespective of the degree of certainty between the observed AE and the drug.

**Unrelated:** An AE does not follow a reasonable temporal sequence from administration of the product and/or there is no reasonable possibility that the drug caused the AE. This assessment includes situations where the AE is related to other factors such as the subject's clinical state, other therapeutic interventions, or concomitant drugs administered to the subject.

Default assessments using the 'related' category without supportive evidence for a causal relationship to study drug are generally uninformative and do not contribute meaningfully to the development of the safety profile of the drug or to subject protection.

Investigators are encouraged to choose the most plausible cause for the event(s) from the following list: medical history, lack of efficacy/worsening of treated condition, study treatment, other treatment (concomitant, or previous), withdrawal of study treatment, administration error, protocol-related procedure, others (specify).

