#### **11.7 Safety Analyses**

Safety analyses will be descriptive in nature.

All AEs will be coded using MedDRA. Treatment-emergent and post-treatment AEs will be summarized by SOC and preferred term for each treatment group. AEs will also be summarized by their maximum severity.

Summaries will also be provided for the following types of AEs:

- SAEs
- AEs of Special Interest (See [Section 10.1.3](#), Adverse Events of Special Interest)
- Related AEs, as determined by the investigator
- AEs leading to early discontinuation of study drug

All Hb related safety endpoints will be tabulated for each treatment groups.

Observed values of continuous and categorical parameters and changes from baseline for continuous parameters to each study visit will be summarized descriptively for vital signs and clinical laboratory results. Graphical displays of selected laboratory parameters will also be provided.

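### Protocol 10.1.1 exempts CKD-related worsening of anemia from AE reporting with no exception for serious events, in conflict with the protocol's other reporting rules

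*Protocol*

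**What the plan says.** The Worsening of Anemia paragraph in Protocol 10.1.1 states: "Worsening of anemia will not be considered an AE unless the worsening of anemia is associated with a cause" other than the subject's CKD. Its reason is that the primary endpoint assesses Hb response, so that "worsening of anemia is captured as part of this efficacy parameter". The only exception concerns cause. Seriousness and discontinuation are not mentioned.

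Other reporting rules bear on the same event:

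- 10.1.1, Abnormal Test Findings: "Any abnormal laboratory value which requires treatment or further diagnostic testing and/or results in discontinuation from study will be reported as an AE".
- 10.1.1, Pre-existing Conditions: such a condition is not an AE "unless the condition worsens or episodes increase in frequency during the AE reporting period".
- 10.1.2: the seriousness criteria, including "In-patient hospitalization or prolongation of existing hospitalization", are applied to an AE. The section also lets the investigator or sponsor judge any other event serious, and resolves doubt between AE and SAE toward SAE.
- 10.3.3: SAEs go to the sponsor within 24 hours of awareness, and all deaths are investigated and reported.
- 10.3.4: the causes an investigator may choose for an AE include "lack of efficacy/worsening of treated condition".
- 11.7: the planned summaries include SAEs and "AEs leading to early discontinuation of study drug".

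**The concern.** Two problems arise from the text.

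First, a site with a subject whose Hb has fallen because of CKD, and who is transfused or withdrawn for it, receives opposite instructions within one section. One paragraph says the event is not an AE; two others say it is. Nothing states which prevails.

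Second, seriousness is built on AE status. If the exemption is followed as written, a subject admitted to hospital for symptomatic CKD anemia has no assured route to an SAE form or to the 24-hour report. Symptoms may not fill the gap, because 10.1.1 asks for the diagnosis to be reported in place of its symptoms, and here the diagnosis is the exempt one.

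Safety compared with epoetin alfa is part of the primary objective (5.1), and loss of anemia control after conversion is foreseeable. In one cohort of the prior hemodialysis study, "and 19% (6 of 31) of subjects withdrew from the study due to worsening anemia" (4.2). What counts as an AE is fixed at the site by the protocol. A later analysis plan cannot recover seriousness and causality assessments that were never collected.

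**Working it through.** **1. The rules applied to one case.** Take a subject with CKD-related worsening of anemia who is hospitalized, treated and survives.

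| Rule | Result |
|---|---|
| 10.1.1 Worsening of Anemia | Not an AE |
| 10.1.1 Abnormal Test Findings (low Hb needing treatment) | AE |
| 10.1.1 Pre-existing Conditions (anemia worsens) | AE |
| 10.1.2 seriousness criteria | Hospitalization qualifies, but the criteria are applied to an AE |
| 10.1.2 judgment clause | SAE if the investigator or sponsor so decides |
| 10.1.2 doubt rule | Settles AE versus SAE, not AE versus no AE |
| 10.3.3 death reporting | Does not apply to a survivor |
| 10.3.4 cause list | Presumes that worsening of the treated condition can underlie an AE |

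The rules conflict on AE status. The remaining SAE route is discretionary, and it competes with an explicit instruction that this event is not an AE.

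**2. Does the stated reason cover serious events?** The primary endpoint (5.3.1) is the change from Baseline to the average Hb over Weeks 10 to 12. A mean Hb cannot record a hospitalization or its seriousness. The Full Analysis Population (11.2) also requires an Hb value in that window, which leaves out earlier withdrawals, although the Randomized population with LOCF (11.5) partly offsets this. The low-Hb safety endpoint for the Main study (5.5) needs Hb below 8.0 g/dL with a fall of at least 0.5 g/dL. A subject hospitalized at 8.2 g/dL would not meet it.

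**3. Scale.** The protocol's figures for withdrawal due to worsening anemia in the prior study (4.2) reproduce:

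- 300 mg daily: 0/30 = 0%
- 450 mg daily: 1/33 = 3.0%
- 450 mg TIW: 6/31 = 19.4% (stated as 19%)
- Daily cohorts pooled: 1/63 = 1.6% (exact 95% interval 0.0 to 8.5%)
- All cohorts: 7/94 = 7.4% (exact 95% interval 3.0 to 14.7%)

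Planned vadadustat subjects, from the study schematic and the ratios in 8.4.1:

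- Low epoetin group: 40 × 6/8 = 30
- High epoetin group: 55 × 9/11 = 45
- Hyporesponder study: 30 × 1/2 = 15
- Total: 30 + 45 + 15 = 90, leaving 35 of 125 on epoetin alfa

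Assuming the prior-study rates carry over, the expected withdrawals for worsening anemia are:

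- Pooled daily rate: 90 × 1/63 = 1.4
- All-cohort rate: 90 × 7/94 = 6.7

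Under the exemption these would be absent from the AE-leading-to-discontinuation table in 11.7. They would still appear in disposition (11.4). The prior-study data as given do not say whether any of the seven withdrawals was serious, so no loss from the SAE table can be calculated.

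**The case against.** The strongest reply is that the exemption is a reasoned choice: an outcome that is itself the efficacy measure is kept out of the AE counts and recorded elsewhere. Much of this stands.

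- A reader might infer that these withdrawals vanish from all discontinuation reporting. They do not. Section 11.4 summarizes reasons for discontinuation by treatment group, and 7.6.3 offers lack of efficacy as a reason. Only the AE-based table loses them.
- A reader might infer that loss of Hb control before Week 10 goes unrecorded. CBC and rescue use are scheduled at every treatment visit (Appendix A). Low-Hb safety endpoints are tabulated by group (5.5, 11.7). ESA rescue and transfusion are secondary endpoints, with reasons captured on the CRF (5.3.2.1, 8.4.9). The study team also reviews safety data regularly (10.6).
- A reader might infer that serious CKD anemia can never become an SAE. The judgment clause in 10.1.2 speaks of any other event, so a route exists, and deaths are reported under 10.3.3. The text is contradictory, not a clean exclusion.
- A reader might infer that the rule flatters vadadustat. It applies to both arms, and the protocol gives no rate of worsening anemia on epoetin alfa. Uneven under-counting is plausible, because vadadustat subjects convert while controls continue at about their prior weekly dose, but it is not shown.
- A reader might apply the TIW rate to everyone: 90 × 6/31 = 17.4. That cohort started on TIW dosing. Here nobody does; only subjects meeting the Week 12 criteria in 8.4.5.2 transition, and they may convert back.

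It can also be argued that the specific exemption overrides the general rules. That is a possible reading, but the protocol does not state it. Nor does any of the alternative capture record a non-fatal hospitalization for anemia as serious, or guarantee that the sponsor hears of it within 24 hours.

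**Conclusion.** The concern holds in a limited form. The exemption in 10.1.1 has no seriousness override, contradicts two other paragraphs of the same section, and sits badly with the cause list in 10.3.4. Followed as written, it leaves a non-fatal hospitalization for CKD anemia with only a discretionary route to SAE status and 24-hour reporting. The stated justification does not reach such events.

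The loss should not be overstated. Withdrawals and loss of Hb control remain visible by arm. About 1.4 to 6.7 withdrawals could be missing from one table, on the assumption that prior-study rates apply to 90 vadadustat subjects. That assumption is rough: this trial adjusts dose differently, the hyporesponder rate is unknown, and the prior rates rest on one and seven events. The number of serious cases and any difference between arms cannot be quantified. The protocol does not describe worsening anemia as the drug's main harm, so the point should not be put that way. It is worth correcting because safety is part of the primary objective and the correction is cheap.

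**What to change.** In 10.1.1, Worsening of Anemia, limit the exemption to non-serious CKD-related worsening. State that worsening of anemia of any cause that meets a 10.1.2 seriousness criterion is reported as an SAE under 10.3.3.

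Add a cross-reference so that Abnormal Test Findings and Pre-existing Conditions agree with the Worsening of Anemia paragraph, and say which rule governs when low Hb leads to discontinuation. Making every such discontinuation an AE is more debatable, since disposition already reports it; what is needed is one stated rule.

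This changes reporting only, not clinical care. It takes a few sentences in an amendment and a memo to sites. The downside is a few more SAE forms and a slightly higher reported SAE rate.
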